## A. STUDY BACKGROUND AND PURPOSE

Under-immunization rates for childhood immunizations in the United States ranges from 8-20%. Previous studies have demonstrated that pediatric patients are most likely to be under-immunized for seasonal immunizations. The aim of this study is to explore the factors and facilitators contributing to measles immunization hesitancy. Secondly, we aim to explore the impact of hypothetical contexts on measles immunization hesitancy. The results of this study may identify potential disparities in measles immunization coverage and potential solutions for resolving those disparities.

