- Is your child immunized against COVID-19 for this season?
- Is your child immunized against RSV for this season?
  - Yes, the mother was immunized for RSV during pregnancy.
  - Yes, the child was immunized for RSV as an infant.
  - No
  - Unsure

All participants who identify that their child is under-immunized for measles (i.e. did not receive 1st MMR immunization at 1 year of age OR 2nd MMR immunization at 4 years of age) will go on to complete a comprehensive survey to assess immunization beliefs, to include:

- Please indicate that you agree or disagree with the below statements when thinking about getting your child up to date with all of their recommended immunizations?
  - Receiving all the recommended vaccines would significantly reduce my child's risk of getting sick (Vaccine Efficacy)
    - Agree or Disagree
  - Receiving all the recommended vaccines would be safe for my child (Vaccine Safety)
    - Agree or Disagree
  - Receiving all the recommended vaccines would be like performing an experiment on them (Vaccine Distrust)
    - Agree or Disagree
  - Receiving all the recommended vaccine will lead to long-term health problems for my child (Vaccine Long-Term Health Problems)
    - Agree or Disagree
  - Receiving all the recommended vaccines would be harmful to my child because of their current medical condition (Child's Medical Condition)
    - Agree or Disagree

- Agree or Disagree
- Receiving all the recommended vaccines is unnecessary because there is less risk now that young children will be infected with the virus or bacteria (Low Risk of Infection)
  - Agree or Disagree
- Receiving all the recommended vaccines is unnecessary because America has reached herd immunity for the virus or bacteria (low risk for infection)
  - Agree or Disagree
- The opinion of my child's doctor or healthcare provider will influence my decision about getting my young child vaccinated (Not recommended by Provider)
  - Agree or Disagree
- Getting children vaccinated against infectious diseases supports the community by stopping the spread of the disease among other children and adults (Stopping Community Spread)
  - Agree or Disagree
- I do not have enough information about all the recommended vaccines to be comfortable giving them to my child (lack of information)
  - Agree or Disagree
- I do not have a health care provider who has offered my child the vaccine (lack of healthcare access)
  - Agree or Disagree

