### **Patient recruitment, enrollment, and progress through the study**

Once a patient is screened and determined to be eligible, the RA will review the patient's ED electronic health record (dashboard or face sheet) and record (on a redcap database) the following de-identified information: race/ethnicity, gender, ESI level, insurance status, and chief complaints. [Please see data collection form/survey for further details collected.]

Collecting de-identified data from patient's charts poses no or minimal risk to the patient and it is generally considered acceptable to do this without previously consenting patients. We will keep this information on all patients, even if they refuse to participate in the survey portion, as this information is helpful to understand who are the patients that refused to participate in the study and who are the patients who did participate in the study to comment on the potential sampling bias. These demographic data are (a) de-identified, (b) readily available, (c) can be collected as a chart review without individual patient consent, (d) are not sensitive information, and (e) for patients who do not want to participate in the survey, are not linked in any way with the study questions. The information collected allows the investigators to compare the demographics of participants and non-participants; and therefore, to ensure that the sample is not biased.

If a patient meets the inclusion criteria, a RA will administer the consent for collection of their name, medical record number, and survey responses.

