### **D. DATA ANALYSIS**

We will collect the following data: Age, Gender, Race, Ethnicity, State of residence, parental age, parental education level, household income, insurance status, parental report of immunization status and the reason for under-immunization if applicable. The sub-investigators will perform the data analysis at Albany Medical Center (AMC) with an AMC approved password protected PC. Storage of files will be on a password protected departmental drive. Use of a password protected master key document to store identifiers separately from other study variables, which will be collected and stored through REDCAPs.

Our primary outcome is the demographic variables and immunization beliefs that are associated with RSV under-immunization. Survey responses will be used to stratify outcomes according to child's age, Gender, Race, Ethnicity, State of residence, parental age, parental education level, household income, insurance status, and sources of health information. The secondary outcome is the improvement in immunization confidence (defined as converting from "definitely not intent, unsure about intent, or probably not intent" to "intent") stratified by patient-centered immunization messaging.

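### Aim 1 survey: the item labelled as provider non-recommendation asks only whether the provider's opinion influences the guardian, so neither answer shows what the provider recommended

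*Protocol*

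**What the plan says.** Under Aim 1 (Protocol, section B), guardians who report a child under-immunized for measles complete a comprehensive survey of immunization beliefs. Its stem, which concerns vaccines in general, begins "Please indicate that you agree or disagree with the below statements when thinking about getting your child up to date with all of their recommended". Thirteen statements are legible in print. Each is answered Agree or Disagree and carries a short label in brackets.

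The statement at issue reads "The opinion of my child's doctor or healthcare provider will influence my decision about getting my young child vaccinated (Not recommended by Provider", where the closing bracket ends the label. No follow-up on what the provider advised is printed.

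Two other statements come near the subject. One is "I do not have a health care provider who has offered my child the vaccine (lack of healthcare access", labelled as access. The other says that vaccination "would be harmful to my child because of their current medical condition (Child's Medical Condition", which records the guardian's own belief.

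Section D then states: "Our primary outcome is the demographic variables and immunization beliefs that are associated with RSV under-immunization". (It names RSV where the survey concerns measles; that is a separate matter.) The same section lists among the data to be collected "parental report of immunization status and the reason for under-immunization if applicable". Section A gives the purpose: "The aim of this study is to explore the factors and facilitators contributing to measles immunization hesitancy".

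**The concern.** The label and the statement name different things. The label describes a circumstance: a provider did not recommend the vaccine. The statement describes an attitude: the guardian's decision responds to what the provider thinks.

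The difference matters because the study sets out to separate factors from facilitators and to suggest solutions. If many guardians agree, the statement as worded suggests that clinicians are useful messengers. Read by its label, the same result suggests that clinicians are failing to recommend the vaccine and that their advice needs correcting. These point to different actions.

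An analyst can rename the variable later. Renaming does not supply an answer on provider non-recommendation if no item collected one.

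**Working it through.** The protocol gives no figure that bears on this point and no arithmetic applies. The check sets the item's wording against its label and then looks for another item that could fill the gap.

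**Step 1. What each answer reveals.** Cross the provider's position with the guardian's attitude:

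| Provider's position | Guardian gives weight to provider's opinion | Answer | True under the label? |
|---|---|---|---|
| Recommended | Yes | Agree | No |
| Recommended | No | Disagree | No |
| Did not recommend | Yes | Agree | Yes |
| Did not recommend | No | Disagree | Yes |

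The answer follows the second column and does not depend on the first. Agree occurs with the label both true and false, and so does Disagree. Reversing the coding therefore does not rescue the label.

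**Step 2. Whether the labels are meant as construct names.** Most of the other labels describe what their statement asks. The statement that the vaccines reduce the risk of illness is labelled efficacy, the one that they are safe is labelled safety, and the one about having too little information is labelled lack of information. Someone reading the data set would reasonably take this label the same way. Unlike a neutral topic tag, it also asserts a particular state of affairs.

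**Step 3. Whether another printed item measures the labelled construct.** Of the 13 legible statements, two come close.

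- The access item asks whether the guardian has a provider who has offered the vaccine. Offering is related to recommending but is not the same, and the item carries its own label.
- The medical-condition item asks what the guardian believes about harm to the child. It does not ask what a provider said.

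The remaining items concern efficacy, safety, distrust, long-term effects, low risk of infection (two items), community spread, information and social barriers (two items). None asks whether a provider recommended the vaccine. The brief survey asks which source communicates vaccine information most effectively, which is again a question about influence.

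**Step 4. Whether this could be an artefact of reading the PDF.** Statement and label stand on one line of current text, so the mismatch is in the plan itself.

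**The case against.** The strongest reply is that guardians see a clear statement and give a valid answer about provider influence, so only a tag is wrong. The protocol has no rule that codes Agree as the provider not having recommended the vaccine. Several labels are topic tags for which agreement favours vaccination, and variable names are commonly settled in an analysis plan or data dictionary. This stands in part. The harm is conditional on the results being reported under the printed label, and a reader should not infer that the protocol commits to doing so.

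Three stronger readings are tempting, and the protocol does not support them.

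- **That provider non-recommendation is never asked.** This is not established. A response line with no statement attached follows the medical-condition item. It may be a page-break repeat or the remains of a lost statement. The recruitment section also says "Please see data collection form/survey for further details collected", and section D lists a reason for under-immunization. A suitable question may sit on a form that is not shown. It would not make the printed label correct.
- **That the primary outcome is compromised.** This is one belief item of 13, and only guardians of under-immunized children answer it. With no up-to-date group answering, the item cannot by itself show an association with under-immunization. Its use is descriptive.
- **That the access item is also in error.** A guardian with a regular doctor who did not offer the vaccine could agree with it, but not having a provider who offered the vaccine is still a reasonable measure of access. Splitting the item would be a refinement.

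**Conclusion.** The point holds, as a minor one. The item labelled as provider non-recommendation measures provider influence, and neither response identifies the labelled construct. This follows from the wording alone and needs no assumption about how many guardians fall into each group. The protocol gives no such shares, so no numerical error rate is offered.

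The consequence rests on two conditions: that results are reported under the printed label, and that no form outside the protocol asks what the provider recommended. If both hold, one descriptive belief item among under-immunized guardians would be misreported, a possible facilitator would appear as a barrier, and the study would have no measure of something it names. If only the first holds, the misreporting remains but the missing information could be found elsewhere. Eligibility, randomisation, the secondary outcome and the comparison of the four messages are unaffected in either case.

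**What to change.** Make two changes to the comprehensive survey in section B.

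1. Keep the existing statement as worded and relabel it *Provider Influence*.
2. Add one agree/disagree statement whose wording matches the old label, for example: *My child's doctor or healthcare provider has not recommended the measles (MMR) vaccine for my child (Not recommended by Provider)*.

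The new statement should say that the provider has not recommended the vaccine, and should not say that the provider advised against it. A provider who stayed silent has not recommended the vaccine but has not advised against it either, so the narrower wording under the same label would create a new mismatch.

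The cost is one extra response on the tablet and one changed label, and nobody is excluded. If enrolment has begun, answers already given to the existing item remain usable and are reported as provider influence. The new item will be available only for guardians surveyed after it is added, so its denominator will be smaller and should be stated. If the form that is not shown already asks what the provider recommended, the relabelling alone is enough.

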- I cannot miss work (have my child miss school) for a doctor's appointment to receive the vaccine (Social barriers)
  - Agree or Disagree
- I do not have transportation to get my child to the doctor's appointment to receive the vaccine (social barriers)
  - Agree or Disagree

– “Do you plan to get your child fully immunized for measles?”

- “Definitely not”
  - “Probably not”
  - “Unsure”
  - “Yes”

*Aim 2: Explore the impact of favorable immunization messaging on parental confidence in the measles in the under-immunized population.*

All guardians who complete the comprehensive survey will be randomized to receive one of four patient-centered immunization messages. The guardian will then be asked again if they plan to immunize their child against RSV this season and if they would accept the immunization if we administer it at the current visit.

- “Would you give your child the measles vaccination at this visit. This vaccine is known to prevent pneumonia that could lead to death and brain swelling that could lead to seizures or deafness?”
  - “Definitely not”
  - “Probably not”
  - “Unsure”
  - “Yes”
- “Would you give your child the measles immunization at this visit. This immunization is known to prevent pneumonia that could lead to death and brain swelling that could lead to seizures or deafness?”
  - “Definitely not”
  - “Probably not”
  - “Unsure”
  - “Yes”
- “Would you give your child the measles shot at this visit. This shot is known to prevent pneumonia that could lead to death and brain swelling that could lead to seizures or deafness?”
  - “Definitely not”
  - “Probably not”
  - “Unsure”
  - “Yes”
- “Would you give your child the measles medicine at this visit. This medicine is known to prevent pneumonia that could lead to death and brain swelling that could lead to seizures or deafness?”
  - “Definitely not”
  - “Probably not”
  - “Unsure”
  - “Yes”

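### The one survey item labelled as lack of healthcare access does not distinguish, among the items shown, guardians with no provider from guardians whose provider has not offered the vaccine

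*Protocol*

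**What the plan says.** Guardians who report that their child is under-immunized for measles go on to a comprehensive survey of Agree/Disagree statements, 13 of which are visible in section B of the protocol. Each has a bracketed label naming the construct. One has the access label: "I do not have a health care provider who has offered my child the vaccine (lack of healthcare access".

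The nearby statements have other labels. The provider statement says that the provider's opinion "will influence my decision about getting my young child vaccinated (Not recommended by Provider". Two practical-obstacle statements are tagged as social barriers: "I cannot miss work (have my child miss school) for a doctor's appointment to receive the vaccine (Social barriers" and "I do not have transportation to get my child to the doctor's appointment to receive the vaccine (social barriers".

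Outside the survey, the research assistant records from the chart "race/ethnicity, gender, ESI level, insurance status, and chief complaints", and the protocol adds "Please see data collection form/survey for further details collected". Section D lists among the data to be collected "parental report of immunization status and the reason for under-immunization if applicable". Section A says that the results "may identify potential disparities in measles immunization coverage and potential solutions for resolving those disparities".

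**The concern.** The statement joins two facts, that the child has a provider and that a provider has offered the vaccine. Disagreeing requires both to be true; agreeing requires only that one of them fail. The label then names the result as an access problem whichever fact failed.

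That matters because the two situations lead to different actions. A family with no provider needs linking to care. A family whose provider has not offered MMR points to provider practice, or to the timing of the offer. A study that hopes to suggest solutions needs to know which group it has found, and the pooled answer does not say. Some guardians who do have a provider could be counted as lacking access.

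**Working it through.** The protocol gives no figure for this item, so there is nothing to reproduce. The check is one of logic, followed by a bound.

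**Step 1. Literal answers by situation.**

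| Guardian's situation | Truthful answer | Code received |
|---|---|---|
| No provider | Agree | Lack of access |
| Provider, vaccine not offered | Agree | Lack of access |
| Provider, vaccine offered | Disagree | None |

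So P(Agree) = P(no provider) + P(provider, not offered).

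**Step 2. Does anything else shown separate the two terms?**

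| Variable | What it measures | Separates them? |
|---|---|---|
| Provider-opinion statement (B) | Whether the provider's view sways the decision | No |
| PCP response option in the brief survey (B) | Which information source is thought most effective | No |
| Missed work or school; transport (B) | Obstacles to attending an appointment | No |
| Insurance status (chart; D) | Coverage, not whether there is a provider or an offer | No |
| Reason for under-immunization (D) | Listed as collected, but no separate question for it is shown | Cannot be judged |

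**Step 3. Can the second group exist under the eligibility rules?** Yes. Eligibility starts at age 1, and under-immunized includes not having had the dose due at age 1. A child who has just turned 1 may have a provider but no offer yet. The survey's statement about the child's medical condition also shows that the protocol anticipates medical concerns, and a provider might have held back an offer for such a reason. How many such guardians there are is not stated.

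**Step 4. Bound.** Let A be the share who agree, and q the share of those who have a provider who has not offered the vaccine. Then:

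- true no-provider share = A × (1 − q)
- reported share ÷ true share = A ÷ [A × (1 − q)] = 1 ÷ (1 − q)

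Neither A nor q is in the protocol. With an assumed A of 20%:

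| q (assumed) | No-provider share | Reported ÷ true |
|---|---|---|
| 0 | 20% × 1 = 20% | 1.00 |
| 0.2 | 20% × 0.8 = 16% | 1.25 |
| 0.5 | 20% × 0.5 = 10% | 2.00 |
| 1 | 20% × 0 = 0% | not defined |

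If the item is answered literally, the error in the no-provider share can go only one way, upwards, and it is zero when q = 0. The table shows how the error depends on q; it is not an estimate for this trial.

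**The case against.** Several points against the concern are sound, and they limit it.

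- **Access is not defined.** A reader might infer that the barrier *is* overstated. That needs access to mean having a provider, and q to be above zero. The protocol says neither. If access means having a provider who makes the vaccine available, agreement measures just that and nothing is inflated. This stands, so only *may be overstated* is supported.
- **The full form is not shown.** A reader might infer that the two causes can never be separated. Section C (recruitment and enrollment) refers to a data collection form outside the document, and section D lists a reason for under-immunization that could be its own field. Consented participants are also linked to a medical record number until the master key is destroyed (section G), although provider status is not among the chart variables listed. The claim therefore has to stay with the items shown.
- **Access is also touched on elsewhere.** The item is the only one with this label, but transport, missed work or school, and insurance status also bear on reaching care. It would be wrong to say that the study has no other access information.
- **No reporting rule is fixed.** A reader might infer that every missed offer will be published as lack of access. The label is a bracketed tag, section D names no access variable, and results could be reported by item wording.
- **The reach is narrow.** This is one of 13 visible statements, asked only of the under-immunized subgroup. Section D's primary outcome names demographic variables and immunization beliefs, and a practical barrier is not clearly either.

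What these points do not remove is the mismatch in section B itself: as labelled, a guardian who has a provider can be coded as lacking healthcare access, and no item shown corrects that. Reporting by item wording would avoid the misleading label but would not separate the two groups.

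**Conclusion.** The concern holds in a limited form. The item pools two situations under one label, and none of the items shown separates them. Lack of access, in the sense of having no provider, may be overstated by an amount that the protocol does not allow anyone to determine: the true share lies between 0 and the share who agree. This rests on literal answers, on that meaning of access, and on the unseen data collection form not already asking the question.

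The consequence is for the interpretation of one Aim 1 barrier item, and for any solution drawn from it. The Aim 2 randomized comparison of messages does not use this item and is unaffected. The change is worth making because it is cheap and serves the study's stated purpose, not because the main results depend on it.

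**What to change.** Replace the item with two, coded and reported separately:

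1. *My child does not have a regular health care provider.* Agree/Disagree; coded as lack of healthcare access.
2. *My child's health care provider has not offered the measles (MMR) vaccine.* Agree/Disagree; coded as not offered by provider; shown only to guardians who disagree with item 1.

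If the data collection form already asks these questions, cite them in section B and correct the label there. If enrolment has begun, keep answers to the existing item as a separate variable, because they cannot be split afterwards from the items shown. If the survey cannot be changed, report the result by the item's wording and not as lack of access.

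The cost is one extra tablet question for guardians in the under-immunized subgroup who have a provider, one branching rule and one additional code.

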## B. STUDY DESIGN

This will be a cross sectional RCT study conducted through web-based surveys to determine factors and facilitators contributing to measles immunization confidence in the ED.

*Aim 1: Identify the characteristics of the measles under-immunized population.* Parents of patients aged 1 year up to and including 6 years of age who present to the AMC pediatric ED between 6/1/2025 and 6/1/2026 will be screened for the below exclusion criteria:

- The patient is critically ill- Any life-threatening condition that requires pharmacological and/or mechanical support of vital organ functions, i.e. shock, moderate to severe asthma exacerbation, airway obstruction, anaphylaxis, etc.
- The patient presents with major (i.e. leveled) trauma
- The patient presents with concern for physical or sexual assault
- The patient presents with need for child protective service evaluation
- The patient or guardian are not English speaking
- The patient presents in custody of a juvenile detention center or law enforcement
- The patient presents without a consenting parent or legal guardian present at time of evaluation

Parents of children meeting the above inclusion and exclusion criteria will be approached for consent to participate in the study by convenience sampling weekdays 0900-1700. All consenting guardians will complete a brief survey to assess parental demographics and child immunization history. The below questions will be included in the brief survey:

- Age of caregiver
- Age of child
- Race of caregiver
- Ethnicity of caregiver
- Education level of caregiver
  - High school degree
  - College/University/technical school degree
  - Post-graduate college/university degree
- Household income level of caregiver
  - <24,000
  - 24,001-53,000
  - 53,001-89,000
  - 89,001-136,000
  - ≥136,001
  - Unknown
- What source do you find to be the most effective at communicating vaccine information
  - Social media
  - PCP (Primary care physician)

- Personal communication with friends/families
- Government agencies (i.e. Center for Disease Control and Prevention)
- Pharmaceutical companies
- On average, how many minutes do you (the guardian) spend on social media outlets per day?
  - 0-30 minutes
  - 31-60 minutes
  - 61-120 minutes
  - 121-180 minutes
  - 181-240 minutes
  - ≥241 minutes
- Is your child up to date with all routine (Not including influenza, COVID-19, RSV) immunizations at this time?
- Is your child immunized against Influenza for this season?

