### **Sample Size Considerations**

We plan to enroll ~800 patients at AMC.

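### One barrier item asks about the guardian's work and the child's school with a single answer, so agreement cannot be attributed to either and its pattern by child's age cannot be interpreted

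*Protocol*

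**What the plan says.** Three parts of the Protocol bear on this point.

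- **The item.** In B. Study Design, the comprehensive survey includes "I cannot miss work (have my child miss school) for a doctor's appointment to receive the vaccine (Social barriers". The only answers offered are "Agree or Disagree". Nothing tells the guardian how to read the parenthesis, and there is no not-applicable answer. The next statement, on transportation, carries the same label but asks about one barrier only.
- **Who answers.** The study recruits "Parents of patients aged 1 year up to and including 6 years of age". The comprehensive survey then goes to "All participants who identify that their child is under-immunized for measles", which the Protocol defines by a first dose due at 1 year or a second due at 4 years. Families of both younger and older children can therefore reach this item.
- **How it is used.** D. Data Analysis says "Our primary outcome is the demographic variables and immunization beliefs that are associated with RSV under-immunization". (That sentence names RSV although the survey concerns measles; this is a separate matter and does not affect the present point.) The same section says "Survey responses will be used to stratify outcomes according to child's age", with child's age first in a list of about ten variables.

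**The concern.** A guardian who cannot leave work and a guardian whose child cannot miss school give the same answer. For a child who is not in school, only the work part can apply. For a child in school, either part may drive the answer, and some guardians may agree only if both are true. The item may therefore measure different things at different ages, and age is a variable by which results are to be broken down.

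Two things are at stake. First, A. Study Background and Purpose hopes that the results may point to solutions for gaps in coverage, and this item cannot show which of the two barriers a solution should address. Second, if agreement differs between younger and older children, the reader cannot tell a difference in work constraints from the presence of a school constraint or from a difference in how the sentence was read.

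Analysis cannot repair this later. Neither the brief-survey questions nor the data list in D. Data Analysis includes the child's school attendance or the guardian's employment. Child's age is recorded, but it is only a proxy for schooling.

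**Working it through.** The plan states no figure on this point, so there is none to reproduce. The check asks what one binary answer can reveal, and whether a difference by age has a predictable size or sign.

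**Inputs from the Protocol.** One statement, one binary answer, children aged 1 to 6, and stratification by child's age.

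**Inputs assumed, because the Protocol gives none.** Let *w* be the share of guardians who cannot miss work, set equal at every age, with range 10–30%. Let *s* be the share of families with a child in school for whom missing school is a barrier, with range 0–20%. A family whose child is not in school is taken to answer on work alone, so its agreement rate is *w*.

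**Step 1: can the two barriers be separated?** Suppose guardians agree if either barrier applies, and the barriers are independent. Agreement among children in school is then 1 − (1 − w)(1 − s).

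- w = 20%, s = 10%: 1 − 0.80 × 0.90 = 28%.
- w = 10%, s = 20%: 1 − 0.90 × 0.80 = 28%.

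The two situations have opposite leading barriers and give the same observed rate. The answer does not identify which barrier matters.

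**Step 2: what age difference results when the work barrier is the same at every age?** The difference is agreement for children in school minus agreement for children not in school.

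| How guardians read the item | Formula for the difference | Result over the assumed ranges |
|---|---|---|
| Work only | w − w | 0 |
| Either barrier, school barrier only in families that also have the work barrier (needs s ≤ w) | w − w | 0 |
| Either barrier, independent | s(1 − w) | +7 points (0.10 × 0.70) to +18 points (0.20 × 0.90) for s = 10–20% |
| Either barrier, no overlap | s | up to +20 points |
| Both barriers required, independent | ws − w = −w(1 − s) | for example −27 points (w = 30%, s = 10%) and −8 points (w = 10%, s = 20%) |
| Both barriers required, extremes | min(w, s) − w | 0 (s ≥ w) to −30 points (s = 0, w = 30%) |

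With no true age difference in the work barrier, the item can show no difference, a positive one or a negative one. The Protocol does not say which reading applies.

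**Step 3: after splitting.** Under the same assumption of equal *w*, a work-only item has an expected age difference of w − w = 0. A school-only item is read only for children in school.

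**Step 4: reach.** The Protocol states "We plan to enroll ~800 patients at AMC". Its background section gives under-immunization of 8–20% for childhood immunizations in general. If that range applied here, 800 × 0.08 = 64 to 800 × 0.20 = 160 guardians would answer the item, before any split by age.

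**The case against.** The strongest counter-argument is that the label marks the item as a general measure of social barriers, not of work alone. If guardians agree when either barrier applies, higher agreement for children in school reflects a real additional obstacle. This stands. A reader might infer that the plan builds in a false age difference, and the documents do not support that. Under the either-barrier reading the extra agreement is real but cannot be separated from work; under other readings the difference is zero or negative.

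A reader might also attach a size to the effect. Assuming independence, with work at 20–40% and school at 10–30%, s(1 − w) runs from 0.10 × 0.60 = 6 to 0.30 × 0.80 = 24 points. These rates are all assumed. Independence is doubtful too, since a weekday appointment may take guardian and child out together. The range also leaves out the zero and negative cases, so it is not an estimate.

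Other limits also stand:

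- The Protocol gives no school-entry age and does not define school. Some guardians may count preschool or daycare, so the link with age is loose.
- It sets no age groups and names no age comparison of this particular item.
- The item is one of 13 legible statements in the comprehensive survey.
- Precision will be low anyway. With two equal age groups and 30% agreement (both assumed), the 95% half-width of a difference is 1.96 × √(2 × 0.30 × 0.70 / n). That is about 22 points for n = 32 per group (64 in all) and 14 points for n = 80 (160 in all).
- The Protocol refers to a separate data collection form that is not shown, so the final tablet layout cannot be checked.

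None of this removes the defect in the wording as printed. Even as a composite, the item leaves open whether one barrier or both are needed to agree.

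**Conclusion.** The point holds, as a minor one. The item is double-barrelled with a single binary answer, and its school part may not apply to the younger children in the 1 to 6 year range. Agreement cannot be attributed to work or to school, and a difference by child's age on this item cannot be interpreted.

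No numerical bias can be claimed. The figures above rest on assumed rates and serve only to show that both size and sign depend on the guardian's reading and on the overlap of the two barriers. The conclusion itself needs only the printed wording, the age range and the listed stratifier.

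The consequence is confined to one descriptive item, asked only of families of under-immunized children. The randomized comparison of the four messages does not use it.

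**What to change.** Replace the item with two agree/disagree statements, for example *I cannot take time off work to bring my child for the vaccine* and *My child cannot be out of school to get the vaccine*. Give the second a third answer, *My child is not in school*. Report the two separately, and use as the denominator of the school item only those guardians to whom it applies.

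The cost is one more statement on the tablet in the comprehensive survey, with no change in sample size or staffing. If the survey is already in use, answers to the combined item should not be pooled with answers to the new ones. They can be reported as a composite, with a note that work and school cannot be separated and that no conclusion is drawn by child's age.
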